	
Phase II
 
In Phase II, up to 295 randomized subjects and 40-50 roll-in subjects will be enrolled at up to 25 sites in the United States (inclusive of sites enrolling subjects in Phase I). No single site will be permitted to enroll more than 20% of all randomized subjects in Phase II.
 
Subjects with indications for TAVI and who meet study eligibility criteria will be randomized 2:1 (stratified by study site) to one of two treatment arms:
 
 • Intervention – TAVI with the TriGUARD 3 CEPD • Control – standard unprotected TAVI. 
Randomization will be stratified by implanted valve type (Medtronic vs. Edwards).
 
No single valve type will be implanted in more than approximately 70% of randomized patients (phase II).
 
Roll-in subjects (a minimum of 2 and a maximum of 3 Roll-ins per-site) will not be randomized, but will undergo TAVI with the TriGUARD 3 device. These cases will be proctored by a Sponsor representative.
 
All subjects will be followed clinically in-hospital and at 30 days, undergo diffusion-weighted MR imaging 2 to 5 days post-procedure, and undergo neurologic (NIHSS) testing pre-procedure, post-procedure (2-5 days post-procedure), and at 30 days. A follow-up phone-call to assess the occurrence of death or stroke will be done at 90 days.
 
The initial randomized cohort will consist of up to 225 subjects. After at least 50% of the initial randomized cohort (approximately 112 subjects) have reached the 30 day primary efficacy endpoint evaluation time point, a sample size reestimation will be performed in case the conditional power of the trial (assessed by the independent biostatistician) is >40% but <80%, subject to approval by the Sponsor. If this analysis determines that more than 225 randomized subjects will be required to ensure adequate study power, enrollment may continue until the required number of subjects have been enrolled, or until the total subject limit for the study has been reached (whichever occurs first).

Primary safety endpoint:	
Combined safety endpoint (modified VARC 2 defined¹) at 30 days, defined as a composite of death, stroke, life-threatening or disabling bleeding, acute kidney injury (stage 2 or 3), coronary artery obstruction requiring intervention, major vascular complication, and valve-related dysfunction requiring repeat procedure.

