	
 Intended performance of the prosthetic heart valve (no prosthesis-patient mismatch (VARC-defined) and mean aortic valve gradient <20 mm Hg or peak velocity <3 m/s, AND no moderate or severe prosthetic valve regurgitation (VARC-defined) (site-reported) 
General Safety, defined as the composite of the following adverse events:
 
 All-cause mortality All stroke (disabling and non-disabling) Acute kidney injury – Stage 3 (including renal replacement therapy) 
Mortality: [evaluated in-hospital and at 30 and 90 days]
 
 All-cause mortality 
 Cardiovascular mortality 
 Neurologic event related mortality Non-cardiovascular mortality 
Myocardial infarction:
 
 Peri-procedural MI (≤72 hours after the index procedure) Spontaneous MI (>72 hours after the index procedure) 
Neurological Events (component and composite):
 
 Stroke (VARC-2 defined) [evaluated in-hospital and at 30 and 90 days] 
 Ischemic stroke Hemorrhagic stroke Undetermined Disabling Stroke (VARC-2 defined) [evaluated in-hospital and at 30 and 90 days] Non-disabling stroke (VARC-2 defined) [evaluated in-hospital and at 30 and 90 days] Transient ischemic attack (TIA) (VARC-2 defined) Overt CNS Injury (NeuroARC³ defined Type 1) [evaluated in-hospital and at 30 and 90 days] Covert CNS Injury (NeuroARC defined Type 2) Neurological dysfunction without CNS injury (NeuroARC defined Type 3) CNS infarction (NeuroARC defined composite neurological endpoint) CNS hemorrhage (NeuroARC defined composite neurological endpoint) 
Bleeding Complications:

--	--

- Life-threatening bleeding (VARC-2)
- Major bleeding
- Minor bleeding

Acute Kidney Injury (AKIN Classification):

- Stage 2
- Stage 3

Vascular Complications:

- Major vascular complications
- Major vascular complications related to TriGUARD 3

SECONDARY EFFICACY ENDPOINTS

Hypothesis-driven Secondary Endpoints (Phase II)

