12-lead ECG ³	X		X		
Concomitant Medications	X	X	X	X	
Pregnancy Test ⁴	X				
Hematology/Chemistry ⁵	X		X		
Cardiac Enzymes ⁶	X ⁶		X ⁶		
CT Imaging ⁷	X				
Cerebral DW-MRI ⁸			X		
NIH Stroke Scale ⁹	X		X	X	
Modified Rankin Scale ⁹	X		X	X	
TAVI		X			
Echocardiography (SOC) ¹⁰			X		
Device deployment		X			
Adverse Events		X	X	X	
Phone call to assess mortality/ Stroke					X

¹ Physical examination to include heart rate, blood pressure, and ischemic/anginal status (CCS or silent ischemia). The screening/baseline assessment must also include NYHA functional capacity, height, and weight.

² If the full screening/baseline review of eligibility criteria is conducted before the day of enrollment, the following repeat review of selected eligibility criteria should be performed on the day of enrollment and randomization (§6.2.1) to confirm study eligibility, using the most recent available laboratory values and clinical assessments: 1) Ensure that the subject has not had symptoms or chemistry results indicating acute myocardial infarction (§6.1.2.1.5); 2) Ensure that the most recent eGFR remains ≥ 30 (§6.1.2.1.10); 3) Ensure that there are no signs of cardiogenic shock (§6.1.2.1.13); and 4) Review the planned approach for TAVI, as certain approaches will make the subject ineligible for the study (§6.1.2.1.1).

³ Screening/baseline ECG may be performed up to 30 days prior to procedure, as long as there have been no intervening signs or symptoms of myocardial ischemia (in which case the ECG should be performed within 24 hours prior to enrollment). The post-procedure ECG must be performed within 24 hours of the procedure or prior to hospital discharge (whichever occurs first).

⁴ Female patients of childbearing potential must have a pregnancy test within 14 days prior to the procedure

⁵ Hematology and chemistry within 14 days prior to the procedure are defined in §7.2.

⁶ For the screening/baseline assessment, cardiac enzymes (CK), isoenzymes CK-MB or troponins obtained up to 14 days prior to the procedure (or on current admission) are acceptable, provided there has been no intervening episode of myocardial ischemia (in which case cardiac enzymes should be confirmed within 24 hours prior to enrollment). Post-procedure CK/CKMB or troponin (preferably CKMB isoenzyme) will be measured post procedure when clinically indicated. If cardiac biomarkers are elevated, they should be repeated per local standard of care.

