7.7 Three-month Follow-up

7.7.1 Phase I:

All subjects in Phase I were expected to return to the clinic at 90 days (\pm 14 days) post-procedure for a clinical evaluation.

The 90 day follow-up visit consisted of the following assessments:

- Physical examination including ischemic / anginal status (CCS or silent ischemia), heart rate, and blood pressure
- Frailty assessment with the Clinical Frailty Scale
- Documentation of any adverse events/ serious adverse events occurring since the previous evaluation
- Current concomitant medication documentation, including antiplatelet and anticoagulant therapy
- NIH Stroke Scale (NIHSS): Neurologic status evaluation using the NIH stroke scale must be performed by a neurologist or a clinical designee (e.g. neurology fellow).
- Modified Rankin Scale (mRS) must be performed by a neurologist or a clinical designee (e.g. neurology fellow).
- A full neurological evaluation should be performed by a neurologist in all patients in whom a stroke or TIA is suspected on the basis of the NIHSS, mRS, or other signs or symptoms.
- A neuropsychological test battery (§16.7), to be administered by a qualified individual. The test battery includes:
 - Montreal Cognitive Assessment (MoCA)
 - Repeatable Battery for the Assessment of Neuropsychological Status (RBANS)
 - Trail Making Test Parts A and B

- The Short Form 36 Health Survey (SF-36)

Note: All clinically significant adverse events should be carefully documented by the research staff using the adverse event data forms. Any clinically-indicated neuroimaging should be forwarded to the MRI Core Laboratory.

7.7.2 Phase II:

In Phase II, a telephone contact at 90 days (\pm 14 days) post-procedure will establish:

- Mortality
- Stroke

If death or stroke is reported, source documentation will be requested from treating facility to enable CEC adjudication of cause of death (cardiovascular [subclassified and neurologic-event related] or non-cardiovascular) and stroke classification according to the protocol-specified definitions.

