In addition, in the final analysis, assessments of study-center and of region effect on the primary safety endpoint will be carried out on the interventional group within the AT population using logistic regressions. A 0.15 level of significance will be used to assess the significance of each of the study center and region effects on the safety endpoint. A non-significant result for each of study centers and regions will support the pooling of patients across study centers and across regions for the primary safety analysis. A significant result will require further inspection of the by-center and by-region results to assess if poolability is appropriate. Note that centers with less than 5 subjects will be pooled with other centers by closest geographic region; this pooling will be carried out prior to the unblinding.

In addition, a logistic regression to assess the consistency of the primary safety endpoint rate across the following categories will also be performed on the interventional arm (separately for Phase I and Phase II) within the AT population:

- Subject gender (male versus female)
- Valve prosthesis type (Edwards vs. Medtronic)

- Operative risk (by Society of Thoracic Surgeons [STS] Risk Score)
- Type and duration of antiplatelet therapy:
 - Pre- and peri-procedural therapy:
 - Protocol-recommended antiplatelet therapy vs. other
 - Maintenance therapy:
 - Dual antiplatelet therapy (DAPT) to 90 days vs.
 - Monotherapy (aspirin or clopidogrel) to 90 days vs.
 - Warfarin with antiplatelet therapy to 90 days vs.
 - Other

As above, a 0.15 level of significance will be used to assess the significance of the difference of the primary safety endpoint rate across the subgroups of each factor.

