- Ischemic – An acute episode of focal cerebral, spinal, or retinal dysfunction caused by infarction of central nervous system tissue
- Hemorrhagic – An acute episode of focal or global cerebral or spinal dysfunction caused by intraparenchymal, intraventricular, or subarachnoid hemorrhage
- A stroke may be classified as undetermined if there is insufficient information to allow categorization as ischemic or hemorrhagic

Stroke definitions (Modified Rankin Scale assessments should be made by qualified individuals according to a certification process):

- Disabling stroke – a mRS score of 2 or more at 90 days and an increase of at least one mRS category from an individual's pre-stroke baseline
- Non-disabling stroke – a mRS score of less than 2 at 90 days or one that does not result in an increase of at least one mRS category from an individual's pre-stroke baseline

Successful device deployment

Ability to access the aortic arch with the TriGuard HDH or TriGUARD 3 delivery catheter and deploy the device from the delivery catheter into the aortic arch.

Successful device retrieval

Ability to retrieve the TriGuard device and remove the TriGuard CEPD.

TAVI device success

Equivalent to the VARC definition¹¹¹ of “device success” for transcatheter aortic valves. Defined as:

- Absence of procedural mortality AND
- Correct positioning of a single prosthetic heart valve into the proper anatomical location AND
- Intended performance of the prosthetic heart valve (no prosthesis-patient mismatch (VARC-defined) and mean aortic valve gradient <20 mm Hg or peak velocity <3 m/s, AND no moderate or severe prosthetic valve regurgitation (VARC-defined)

Technical success

Successful TriGuard HDH or TriGUARD 3 device deployment, device positioning, and successful device retrieval in the absence of device interference

Total procedural time	Time elapsed between first arterial access and removal of the last catheter from the arterial access sheath

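### Phase II schedules no 90-day mRS or medication record, yet stroke severity and the maintenance antiplatelet strata are defined by day-90 data

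*Combined protocol and SAP*

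**What the plan says.** Appendix I (Section 16.1, VARC-2 stroke) calls a stroke disabling on "a mRS score of 2 or more at 90 days and an increase of at least one mRS category" relative to the pre-stroke baseline. It calls a stroke non-disabling on "a mRS score of less than 2 at 90 days or one that does not result in an increase of at least one mRS category". It adds that mRS ratings should come from qualified individuals under a certification process.

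The Synopsis lists "Disabling Stroke (VARC-2 defined) [evaluated in-hospital and at 30 and 90 days" as a secondary safety endpoint, with non-disabling stroke at the same time points. Section 5.4.2.1.2 repeats both.

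For Phase II the Synopsis says "A follow-up phone-call to assess the occurrence of death or stroke will be done at 90 days". Section 7.7.2 begins "In Phase II, a telephone contact at 90 days" and lists mortality and stroke as the two things to establish. In Table 7a the "Modified Rankin Scale" row is marked at baseline, post-procedure and 30 days. The medication row is marked at baseline, procedure, post-procedure and 30 days. The only item in the 90-day column is "Phone call to assess mortality/ Stroke".

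Section 12.4.2 tests the consistency of the primary safety endpoint across maintenance regimens, the first being "Dual antiplatelet therapy (DAPT) to 90 days vs" the others (monotherapy, or warfarin with antiplatelet therapy, over the same period, and a residual class). Section 12.4.3 applies the same classes to the efficacy components. Both analyses are run separately for each phase at the 0.15 level.

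**The concern.** Two sets of rules call for day-90 measurements that Phase II does not schedule. The likely origin is visible in the version history: version 11 replaced the 90-day visit with a call, and the definitions and strata that depended on the visit were left as they were.

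For a device meant to prevent stroke, the severity of the strokes that occur is an important safety description. As written, it would rest on a scheduled measurement in Phase I and on whatever outside records happen to contain in Phase II.

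The strata have a second problem that complete data would not cure. The outcomes are known by day 30, but the class is settled only at day 90. Death and life-threatening bleeding are components of the safety endpoint, and either can end or alter antiplatelet therapy. Class membership can therefore depend on the outcome whose consistency is being tested.

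**Working it through.** The plan states no expected number of disabling strokes, so there is no figure to reproduce. The check compares what is required with what is scheduled, then sizes the gap.

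**1. Required against scheduled**

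| Item | Required by | Phase I (Table 7, 7.7.1) | Phase II (Table 7a, 7.7.2) |
|---|---|---|---|
| mRS at day 90 | Appendix I, both severity classes | Scheduled | Not scheduled; last at 30 days |
| Maintenance therapy to day 90 | 12.4.2, 12.4.3 | Medications scheduled at 90 days | Not scheduled; last at 30 days |
| Pre- and peri-procedural therapy | 12.4.2, 12.4.3 | Scheduled | Scheduled |
| Death and stroke at day 90 | Synopsis, 5.4.2.1.2 | Scheduled | Scheduled (call) |

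Only the first two rows fail. Because Appendix I gives one definition for all time points, the in-hospital and 30-day reports of severity also depend on the day-90 score.

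**2. Uncovered interval**

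The 30-day visit window is 30 ± 7, so the last scheduled record falls on day 23 to 37. The time left to day 90 is 90 − 37 = 53 to 90 − 23 = 67 days.

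**3. Strokes affected**

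Assumption: the weighted 30-day stroke rates in Table 11a apply (5.09% device, 7.25% control).

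- Initial cohort of 225 (150 and 75): 150 × 0.0509 + 75 × 0.0725 = 7.6 + 5.4 = about 13.
- Maximum of 295 (about 197 and 98): 10.0 + 7.1 = about 17.
- Roll-ins: 40 × 0.0509 = 2.0 to 50 × 0.0509 = 2.5.

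A subject who dies after a stroke scores mRS 6 (Appendix I), and mortality is collected to day 90. Such a stroke meets the disabling definition without an interview. Section 4.1.2.1 cites a meta-analysis with 25.5 ± 21.9% 30-day mortality after stroke. On that basis 13.1 × (1 − 0.255) = about 10 of the initial cohort's strokes would be in survivors. Over the reported ± interval the range is 13.1 × 0.526 = 7 to 13.1 × 0.964 = 13. The documents give no Phase II rate for strokes between day 30 and day 90, so those are not counted.

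**4. Order of events for the strata**

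The safety endpoint is complete at day 30, and the efficacy components at days 2 to 5 or day 30. A class defined by therapy to day 90 is fixed later. Neither 12.4.2 nor 12.4.3 says where a subject belongs who dies, or whose therapy changes, before day 90. The gap touches every Phase II subject in the maintenance comparison.

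**The case against.** The strongest reply is that the plan gives other routes to the information.

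- **Stroke records.** Section 7.7.2 goes on to request treating-facility documents after a reported death or stroke, so that the CEC can classify it by the protocol's definitions. Section 11.2 leaves source-document requirements to the CEC Charter, and Section 12.1 leaves endpoint clarifications to the SAP. Either may hold a rule that the text reviewed here does not show.
- **mRS.** Sections 7.2 and 7.5 call for the mRS at every follow-up assessment.
- **Medication.** Section 9.9.1 collects clinically significant adverse events up to the 90-day call, Section 9.8.4 records drug changes made for an event, and Section 7.3 asks for all medications to be recorded in the CRF.

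This stands in part. It rules out saying that severity can never be classified. It does not supply the missing inputs. Nothing requires outside records to contain a day-90 mRS, let alone one by a qualified rater blinded as Section 6.3 asks. If the call counts as a follow-up assessment, Sections 7.2 and 7.5 contradict Table 7a and 7.7.2. Event-driven drug entries do not make a day-90 regimen for subjects without events.

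Several stronger readings are tempting but not supported:

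- **Every Phase II stroke is unclassifiable.** Deaths are mRS 6.
- **As many as 20 strokes are affected.** This needs about 9%, a control-arm rate, in all 225 subjects (225 × 0.09 = 20). The plan's own assumed rates for death or stroke give only 150 × 0.06 + 75 × 0.11 = about 17 events in total.
- **Early deaths and bleeds all land in the residual class.** No allocation rule is documented, so neither the class nor the direction of any bias is known.
- **Pooling of Phase I controls is compromised.** Sections 12.2.4 and 12.4.3 discuss pooling for the primary efficacy endpoint, which counts any stroke.

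**Conclusion.** The concern holds as an unreconciled mismatch between definitions and schedule. For Phase II stroke survivors, severity cannot be reliably derived as defined, and the two phases would be classified from different data. The size is modest: about 13 strokes in the initial 225 at the Table 11a rates, of which perhaps 7 to 13 are in survivors. The maintenance strata cannot be derived from scheduled Phase II data. They are also fixed after the outcome, with no rule for early death or change of therapy.

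The reach is limited. Both primary endpoints and the hypothesis-driven stroke endpoints count any stroke, so a reader should not infer that trial success is at risk. Disabling stroke is reported descriptively. The maintenance regimen is one of several consistency factors, and no stated decision follows from it. The change should be made because a prespecified safety endpoint lacks its defining measurement.

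The stroke counts assume the Table 11a rates. The rest follows from the text and assumes that no rule in the CEC Charter or SAP fills the gap.

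**What to change.** 1. **Stroke severity, one of two options.** The stronger option is to give the Appendix V structured mRS interview at the existing 90-day call to subjects who have had a stroke, by a qualified rater blinded to allocation, and to add it to Table 7a and 7.7.2. This keeps the definition and covers strokes after the 30-day visit. Alternatively, define and label severity by the 30-day mRS, which both phases collected, for strokes up to that visit, and report later strokes as severity not classified. The 30-day score alone cannot classify those.

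2. **Maintenance strata.** For the 30-day endpoints, replace the day-90 classes with the regimen recorded at the post-procedure assessment (Section 7.5). Table 7a has no discharge column, so the time point should be named as post-procedure. State that the factor no longer measures duration, and say how subjects who die before that record are handled.

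3. **Reconcile together.** Align Appendix I, the Synopsis and 5.4.2.1.2 endpoint lists, Sections 7.2 and 7.5, Table 7a, Section 7.7.2, and Sections 12.4.2 and 12.4.3.

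The cost is wording plus, under the first option, a short interview within an existing call for roughly the number of stroke survivors shown above. No visit is added. The second option and the new strata use data already scheduled.

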16.2 Appendix II: Acronyms

AE	adverse event
ADE	adverse device effect
AF	atrial fibrillation
ALT/SGPT	alanine transaminase / serum glutamic pyruvic transaminase
AKI	acute kidney injury
AMI	acute myocardial infarction
ANOVA	analysis of variance
AS	aortic stenosis
ASA	acetylsalicylic acid
ASADE	anticipated serious adverse device effect
AST/SGOT	Aspartate transaminase / serum glutamic oxaloacetic transaminase
AT	As treated
BARC	Bleeding Academic Research Consortium
BAV	balloon aortic valvuloplasty
BUN	blood urea nitrogen
CABG	coronary artery bypass graft surgery
CCS	Canadian Cardiovascular Society
CEC	clinical events committee
CEPD	Cerebral Embolic Protection Device
CI	confidence interval
CIP	clinical investigation plan
CK	creatinine kinase
CK-MB	creatinine kinase-MB fraction
CNS	central nervous system
CRF	case report form

CT	computed tomography
DAPT	dual antiplatelet therapy
DICOM	Digital Imaging and Communications in Medicine
DSMB	data and safety monitoring Board (Interchangeable with DSMC)
DW-MRI	diffusion-weighted magnetic resonance imaging
EC	Ethics Committee
ECG	electrocardiogram
EDC	electronic data capture (system)
EDD/EPD	embolic deflection device/embolic protection device (see also CEPD)
eGFR	estimated Glomerular Filtration Rate
eITT	efficacy Intention to Treat
EU	European Union
F	french (catheter scale system)
FDA	U.S. Food and Drug Administration
GCP	good clinical practices
GI	gastrointestinal
ICH	International Conference on Harmonization
INR	international normalized ratio
IQR	interquartile range
IRB	Institutional Review Board
ISO	International Organization for Standardization
ITT	intention to treat
IV	intravenous
LAO	left anterior oblique
LBBS	left bundle branch block

LV	left ventricle/left ventricular
MACCE	major adverse cardiovascular and cerebrovascular events
MDRD	Modification of Diet in Renal Disease
MI	myocardial infarction
MoCA	Montreal Cognitive Assessment
MRI	magnetic resonance imaging
mRS	modified Rankin Scale
NeuroARC	Neurologic Academic Research Consortium
NIHSS	National Institutes of Health Stroke Scale
NYHA	New York Heart Association
OPC	objective performance criterion
PCI	percutaneous coronary intervention
PP	per protocol
PPM	prosthesis-patient mismatch
PT	per treatment
PTT	partial thromboplastin time
QD	quaque die (daily)
RBANS	Repeatable Battery for the Assessment of Neuropsychological Status
RBC	red blood cells
RI	roll-in
SADE	serious adverse device effect
SAE	serious adverse event
SAVR	surgical aortic valve replacement
SD	standard deviation
SF-36	Short Form 36 Health Survey
SOC	standard of care

STS	Society of Thoracic Surgeons
TAVI	transcatheter aortic valve implantation
TEE	transesophageal echocardiography
TIA	transient ischemic attack
UADE	unanticipated adverse device effect
URL	upper reference limit
US	United States
VARC	Valve Academic Research Consortium
WBC	white blood cell

